6.5.4.4 TGFβ Inhibition Mediated Skin Reactions

Skin assessments are performed at Screening period and every 6 weeks for all subjects per Schedule of Activities (see [Table 1](#) **Error! Reference source not found.**).

Skin AEs, possibly due to TGFβ inhibition, including hyperkeratosis, KA, and/or cSCC, are AESIs and important identified risks for MSB0011359C. The distribution of lesions tends to be in sun-exposed areas.

Management guidelines for potential TGFβ inhibition mediated skin reactions are:

1. Discontinuation or interruption is not required in most cases. Continuation of treatment should be evaluated by the Investigator.
2. Emollients may continue to be used.
3. Diagnostic and treatment plan should be developed in collaboration between Investigator and dermatologist. In general, treatment of TGFβ mediated skin lesions such as hyperkeratosis, KA and cSCC should be based on local guidelines/SoC. Lesion evaluation should include excision biopsy of one representative lesion to confirm diagnosis.
4. Treatment and Follow-up for KA and cSCC will depend on number and localization of lesions.
 - For single lesions: Full excision may be recommended.
 - In case of multiple lesions or location not suitable for full excision, other treatment options may be offered by the dermatologist, such as:
 - Mohs surgery, cryotherapy, or other standard treatment options depending on the pathology
 - Use of retinoids, if recommended by dermatologist, may be considered after discussion with Medical Monitor.
5. Close clinical Follow-up for re-evaluation, resolution, or potential recurrence should be implemented.

6. Spontaneous resolution of KA lesions without surgical intervention has been observed, typically occurring within weeks after discontinuing MSB0011359C.

Consult with study Medical Monitor, as needed, for management of TGF β mediated skin lesions.

6.5.4.5 Anemia

Risk management measures in addition to routine laboratory tests will include:

- Subjects must enter the study with Hgb values at least 9 g/dL
- Routine monitoring of Hgb, red blood cells, and hematocrit will be performed every week up to Week 5 and then every 2 weeks thereafter (prior to treatment)
- Instructions for study treatment discontinuation or modification in case of anemia will be provided, briefly described here:
 - During the 21-Day-DLT period, a grade 3 Hgb decrease (< 8.0 g/dL) requires treatment discontinuation, unless it resolves to at least 9 g/dL within 14 days or changes in associated red blood cell parameters during such a Hgb decrease that resolve within 14 days without blood transfusion or erythroid growth factor use. However, if after the 21-Day-DLT period the subject experiences a Grade 3 Hgb decrease (< 8.0 g/dL) that is clinically manageable with blood transfusions or erythroid growth factor use, this does not require treatment discontinuation
 - Especially if Hgb < 7 g/dL, the Investigator should consider blood transfusion
 - In case of any Hgb < 8 g/dL, the Investigator should use discretion to initiate anemia work up, including Coombs, haptoglobin, indirect bilirubin and peripheral smear, and prothrombin time (PT), activated partial thromboplastin time (aPTT), international normalized ratio (INR); Hgb, red blood cells, and hematocrit are to be closely monitored
- If a subject experiences significant anemia, then the amount of blood to be drawn may be reduced by not taking blood at selected time points for PD-L1 target occupancy, immunomonitoring, soluble factors, and TGF β . The decision to reduce the time points for these biomarkers will be taken by the Investigator in consultation with the Medical Monitor. This will be documented. Blood will continue to be taken as scheduled for safety analyses, PK, and ADAs.

6.5.4.6 Bleeding Adverse Events

Mucosal/Non-tumor Bleeding

If a Grade 2 treatment-related TEAE improves to Grade \leq 1 or completely resolves by the day before the next infusion, study intervention may be continued.

If a Grade 2 treatment-related non-tumor bleeding does not improve to Grade \leq 1 or completely resolve by the day before the next infusion, but it is manageable and/or not clinically relevant, the Medical Monitor should be consulted to assess if it is clinically reasonable to administer the following infusion.

For Grade 3 non-tumor bleeding, study treatment must be permanently discontinued unless an alternative explanation can be identified (such as concomitant use of antithrombotic agents, traumatic event, etc.). In case of alternative explanations for the Grade 3 bleeding event, study treatment should be held until the event recovers to Grade ≤ 1 .

For Grade 4 non-tumor bleeding, treatment must be permanently discontinued if no alternative explanation is identified.

Tumor Bleeding

For Grade ≥ 2 tumor bleeding, study treatment must be held until the event recovers to Grade ≤ 1 . Treatment should be permanently discontinued if the Investigator considers the participant to be at risk for additional severe bleeding.

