3.5.5 Bleeding Adverse Events

Mucosal/Non-tumor Bleeding

Bleeding AEs are AESIs and considered important identified risk. Participants treated with MSB0011359C were commonly reported with mild to moderate mucosal AEs such as epistaxis, hemoptysis, gingival bleeding and hematuria. In general, these reactions resolve without discontinuation of treatment. See Section 6.5.4 for risk management measures.

Tumor Bleeding

Participants treated with MSB0011359C were reported in lower frequencies, with Grade ≥ 3 hemorrhages including tumor bleeding.

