5.1.7.2 Adverse Drug Reactions Requiring Treatment Discontinuation

Certain ADRs, defined as an AE assessed as related to MSB0011359C by the Investigator and / or Sponsor, may require permanent treatment discontinuation of MSB0011359C (listed below). For certain ADRs assessed to be immune-related, [Table 7](#) criteria may supersede this section. These criteria may allow the subject to continue on study if medically indicated after consultation with Medical Monitor.

Any Grade 4 ADRs require permanent treatment discontinuation except for single laboratory values out of normal range that do not have any clinical correlate and resolve to Grade \leq 1 or Baseline grade within 7 days with adequate medical management.

Any Grade 3 ADRs require treatment discontinuation except for any of the following:

- Transient (\leq 6 hours) Grade 3 flu-like symptoms or fever, which is controlled with medical management.
- Transient (\leq 24 hours) Grade 3 fatigue, local reactions, headache, nausea, emesis that resolves to \leq Grade 1 or Baseline grade.
- Tumor flare phenomenon defined as local pain, irritation, or rash localized at sites of known or suspected tumor.
- Any Grade \geq 3 drug-related amylase or lipase abnormality that is not associated with symptoms or clinical manifestations of pancreatitis. The Study Medical Monitor should be consulted for such Grade \geq 3 amylase or lipase abnormalities. If the amylase or lipase abnormality not associated with symptoms or clinical manifestations of pancreatitis has not resolved to Grade \leq 1 within the subsequent 2 cycles (28 days), the subject should permanently discontinue treatment with MSB0011359C unless approved to continue by Medical Monitor after specific request from site Investigator.
- Grade 3 Hgb decrease ($<$ 8.0 g/dL) that is clinically manageable with blood transfusions or erythroid growth factor use does not require treatment discontinuation. During the 21-Day-DLT period, a Grade 3 Hgb decrease ($<$ 8.0 g/dL) requires treatment discontinuation, unless it resolves to at least 9 g/dL within 14 days or changes in associated red blood cell parameters during such a Hgb decrease that resolve within 14 days without blood transfusion or erythroid growth factor use.

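### For a drug-related Grade 3 or 4 tumor bleed, protocol Sections 5.1.7.2 and 5.5.1 require discontinuation while Section 6.5.4.6 requires a hold until recovery, and nothing says which governs

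*Protocol*

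**What the plan says.** **General rule.** Section 5.1.7.2 concerns adverse drug reactions (ADRs), each "defined as an AE assessed as related to MSB0011359C by the Investigator and / or Sponsor". For Grade 4: "Any Grade 4 ADRs require permanent treatment discontinuation except for single laboratory values out of normal range that do not have any clinical correlate" and that settle within a week. For Grade 3: "Any Grade 3 ADRs require treatment discontinuation except for any of the following", followed by a list. The section allows Table 7 to override it for certain immune-related reactions and names no other text that may do so. Section 5.5.1 makes Grade 3 or higher ADRs a reason for withdrawal from treatment, with exceptions only as Section 5.1.7.2 provides.

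**Bleeding rule.** Section 6.5.4.6 treats non-tumor and tumor bleeding separately.
- Grade 3 non-tumor bleeding: "non-tumor bleeding, study treatment must be permanently discontinued unless an alternative explanation can be identified". Grade 4 is handled in a similar way.
- Tumor bleeding of Grade 2 or higher: "tumor bleeding, study treatment must be held until the event recovers to Grade" 1 or lower. The next sentence reads: "Treatment should be permanently discontinued if the Investigator considers the participant to be at risk for additional severe bleeding".

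**Status of the risk.** Section 3.5.5 states: "Bleeding AEs are AESIs and considered important identified risk". It adds that hemorrhages of Grade 3 or higher, tumor bleeding included, have been reported at lower frequencies.

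**The concern.** One event can meet both rules. If a subject bleeds from the tumor at Grade 3 or 4 and the Investigator or Sponsor judges the event related to study drug, Sections 5.1.7.2 and 5.5.1 take the subject off treatment. Section 6.5.4.6 puts treatment on hold until recovery and makes permanent discontinuation depend on a judgement about future risk, not on grade or relatedness.

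Two investigators could each follow the protocol and manage the same serious event in opposite ways. Either could then be cited for a deviation from the section not followed. Because the event belongs to an identified drug risk, this matters for subject safety and for uniform conduct.

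**Working it through.** There is no figure to reproduce; the check is a comparison of texts.

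**Step 1. Apply each rule to each type of tumor bleed.**

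| Tumor bleed | Sections 5.1.7.2 and 5.5.1 | Section 6.5.4.6 | Conflict with the Grade 3/4 rule? |
|---|---|---|---|
| Related, Grade 4 | Permanent discontinuation; the only exception is for isolated laboratory values | Hold to Grade 1 or lower; permanent stop on Investigator's judgement of risk | Yes |
| Related, Grade 3 | Discontinuation unless on the exception list | Same as above | Yes |
| Related, Grade 2 | Outside the Grade 3/4 rule | Same as above | No |
| Unrelated, Grade 3 or 4 | Not an ADR, so the rule does not apply | Same as above | No |

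**Step 2. Look for a bleeding exception.** The Grade 3 list covers flu-like symptoms or fever; short-lived fatigue and similar complaints; tumor flare; amylase or lipase changes; hemoglobin decrease; ECOG performance status; keratoacanthoma and squamous cell carcinoma of the skin; dermatological immune-related events; endocrinopathies; and other immune-related reactions. Bleeding is absent. Tumor flare is the nearest item, but it is limited to local pain, irritation or rash.

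**Step 3. Look for an order of precedence.**
- Section 5.1.7.2 gives that role only to Table 7.
- Section 5.1.7.1 points to Sections 5.1.7.2 and 6.5.4 together for dose delays and does not rank them.
- The closing items of Section 5.1.7.2 send infusion reactions, anemia and immune-related reactions to their own guidance. They do not mention bleeding.

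**Step 4. Test whether the two rules divide by relatedness.** In Section 6.5.4.6 the non-tumor rules do address cause: Grade 2 is limited to treatment-related events, and Grades 3 and 4 turn on an alternative explanation. The tumor rule beside them does neither. Unrelated Grade 3 and 4 events also have a section of their own, 6.5.4.8. So the text does not confine the tumor rule to unrelated bleeds.

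**Step 5. Look at how the conflict may have arisen.** Appendix 4 records Section 6.5.4.6 as added between Versions 7.1 and 7.2 and has no entry for Section 5.1.7.2 among the main changes. Section 5.1.7.2 still sends anemia to Section 6.5.4.4, which now covers skin reactions; anemia is in 6.5.4.5. This suggests that Section 5.1.7.2 was not aligned when 6.5.4 was restructured, though it does not prove it.

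**The case against.** **Resumption is never granted.** Elsewhere the protocol usually says so when treatment may restart, as in Table 7, parts of Section 5.1.7.2 and Section 6.5.4.8. Section 6.5.4.6 could be read as a minimum hold for every tumor bleed, with Section 5.1.7.2 still deciding discontinuation when the bleed is an ADR. This reading is possible, and it is right that resumption is only implied by a hold that ends on recovery. But no text states that reading, and the section's own sentence on permanent discontinuation uses a different test from Section 5.1.7.2.

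**Tumor bleeds may often be judged unrelated.** Relatedness is assessed event by event, and Section 7.4.1.1 counts the course of the underlying disease among the factors. Bleeding's status as an identified risk does not make every tumor bleed drug-related. The sentence quoted from Section 3.5.5 also sits under its non-tumor subheading, although Section 3.5 lists bleeding events in general. This objection limits how often the conflict arises. It does not remove it for a bleed that is judged related.

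**The reach is narrow.** A reader might infer that every cohort is affected. The documents do not show this. The version carrying the bleeding section is 7.2-BE-ES-IT-FR of 22 June 2021, and Section 5.1.1.1 places dose escalation in the USA only. Planned last subject out was Q4 2021. This objection stands.

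**No planned result is shown to be affected.** A reader might also infer that exposure and discontinuation rates would become site-dependent. The SAP does not support that step. Its addendum cutoff is 14 May 2021 and the clinical study report's is 15 May 2020, both before the amendment. SAP Section 6.1 cancels the addendum analyses, Section 7 drops the final analysis after database lock, and Section 15.1.2 does not report events leading to treatment discontinuation. This objection also stands.

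**Conclusion.** The protocol is wrong as written: this is an internal inconsistency, not a design choice. It holds for one defined case, a Grade 3 or 4 tumor bleed assessed as drug-related. It would be tempting to extend it to all tumor bleeding from Grade 2 upward, but the Grade 3/4 rule does not reach Grade 2 events or unrelated events.

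The Investigator-judgement sentence in Section 6.5.4.6 narrows the gap, since some of these subjects would stop treatment under either rule. It does not close the gap, because the trigger is not grade or relatedness.

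The size cannot be given. The documents state neither the frequency of related Grade 3 or 4 tumor bleeding nor the number of subjects still treated under this version. The conclusion rests on reading the hold as ending at recovery, and on the absence of any precedence clause for bleeding. What is at stake is consistent and safe management of those subjects, not bias in a reported estimate.

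**What to change.** Reconcile Section 6.5.4.6 with Sections 5.1.7.2 and 5.5.1:
- state which section governs a Grade 3 or 4 tumor bleed assessed as drug-related;
- say explicitly whether treatment may restart once the hold ends;
- add the matching cross-reference in Sections 5.1.7.2 and 5.5.1, on the model already used in 5.1.7.2 for Table 7;
- correct the anemia reference in Section 5.1.7.2 in the same edit.

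Which clinical rule should apply is for the sponsor's clinical team; this review takes no position on it. The cost is protocol wording only, with no change to sample size, data collection or analysis.

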6.5.4.7 Alterations in Wound Healing or Tissue Damage Repair

Management should be discussed with the Medical Monitor on a case-by-case basis. Dermatological consults should be requested as needed.

6.5.4.8 Dose Interruptions for Adverse Events Not Related to Study Drug

In case of Grade 3 and Grade 4 AEs not study drug related, the study treatment may be interrupted based on the Investigator assessment and the subject will be medically treated for the event.

If the AE reduces to a lower tolerable grade the study treatment might be resumed in the subsequent cycle. If the AE remains the same in spite of medical treatment until the next treatment (second cycle after the AE occurred) a discussion with the Medical Monitor should occur and consideration of a possible extension of the dose interruption for up to 1 additional cycle or a permanent withdrawal from the study treatment should be considered.

If upon the resumed study treatment the subject experiences the same AE this should be rediscussed with the Medical Monitor to assess permanent withdrawal from the study treatment.

Grade 3 and 4 laboratory abnormalities that do not have clinical significance do not require dose interruption.

6.6 Packaging and Labeling of the Investigational Medicinal Product

MSB0011359C freeze-dried formulation is presented at a concentration of 45 mg/vial in USP and Ph Eur type I glass vial closed with a rubber stopper and sealed with an aluminum crimping cap. MSB0011359C liquid formulation is presented at a 10 mg/mL concentration in a USP / Ph Eur type I 50R vial closed with a rubber stopper and sealed with an aluminum crimp seal closure. The stopper is made of elastomer complying with USP and Ph Eur. Vials are filled with 61.2 mL of drug product solution in order to allow an extractable volume of 60 mL.

Packaging and labeling will be in accordance with applicable local regulatory requirements and applicable Good Manufacturing Practice guidelines. MSB0011359C will be packed in boxes containing a suitable number of vials. The information on the medication will be in accordance with approved submission documents.

MSB0011359C will be shipped in transport cool containers [CCI] are monitored with temperature control devices.

6.7 Preparation, Handling, and [CCI] of the Investigational Medicinal Product

MSB0011359C drug product should be stored [CCI] until use. MSB0011359C must not be frozen and should be stored in the original packaging.

Additional instructions for the preparation, handling, storage, and disposal of MSB0011359C will be provided in the Pharmacy Manual.

MSB0011359C must not be used for any purpose other than the study. The administration of IMPs to subjects who have not been enrolled into the study is not covered by the study insurance.

The contents of the MSB0011359C vials are sterile and nonpyrogenic, and do not contain bacteriostatic preservatives. Any spills that occur should be cleaned up using the facility's standard cleanup procedures for biologic products.

Any unused portion of the solution should be discarded in biohazard waste disposal with final disposal by accepted local and national standards of incineration.

6.8 Investigational Medicinal Product Accountability

The Investigator (in Japan, head of the study site) is responsible for ensuring IMP accountability, including reconciliation of drugs and maintenance of records. In Japan, the head of the study site can delegate the control of and accountability for the IMP to an investigational product storage manager.

- Upon receipt of IMP, the responsible person (in Japan, the head of the study site or the investigational product storage manager) will check for accurate delivery and acknowledge receipt by signing or initialing and dating the appropriate documentation and returning it to the location specified. A copy will be archived for the Investigator Site File.
- IMP dispensing will be recorded on the appropriate drug accountability forms so that accurate records will be available for verification at each monitoring visit.
- Trial site IMP accountability records will include the following:
 - Confirmation of IMP receipt, in good condition and in the defined temperature range.
 - The inventory of IMP provided for the clinical trial and prepared at the site.
 - The use of each dose by each subject.

-
- The disposition (including return, if applicable) of any unused IMP.
 - Dates, quantities, batch numbers, vial numbers, expiry dates, formulation (for IMP prepared at the site), and the individual subject trial numbers.

The Investigator site should maintain records, which adequately document that subjects were provided the doses specified in this protocol, and all IMPs provided were fully reconciled. In Japan, the head of the study site should maintain records that all IMPs provided were fully reconciled.

Unused IMP must not be used for any purpose other than the present trial. No IMP that is dispensed to a subject may be redispensed to a different subject.

The Sponsor's Monitor will periodically collect and review the IMP accountability forms and where applicable, will check all returns (both unused and used containers) before arranging for their return or authorizing their destruction by the trial site.

At the conclusion or termination of this trial, trial site personnel and the Clinical Trial Monitor will conduct a final product supply inventory on the Investigational Drug Accountability Forms and all unused containers will be destroyed. Instructions for destruction of product will be provided to the site. The Clinical Trial Monitor will be supplied with a copy for filing of the Investigational Drug Accountability Forms. This documentation must contain a record of clinical supplies used, unused, and destroyed and shall include information on

- all administered units,
- all unused units,
- all destroyed units (during the trial),
- all destroyed units at the end of the trial,
- date of destruction(s),
- name and signature of the Investigator / pharmacist / head of the study site or the investigational product storage manager.

It must be ensured at each trial site that the IMP is not used

- after the expiry date, and
- after the retest date unless the IMP is reanalyzed and its retest date extended.

This is to be closely monitored by the Clinical Trial Monitor.

Destruction of used and unused study intervention(s) should be performed at site if allowed by local law only after Sponsor authorization. If that is not possible, the Sponsor/designee will be responsible.

Further guidance and information for the final disposition of unused study intervention(s) are provided in the Pharmacy Manual.

6.9 Assessment of Investigational Medicinal Product Compliance

In this trial, subjects will receive IMP (MSB0011359C IV infusions) at the investigational site. Well-trained medical staff will monitor and perform the IMP administration. The information of each IMP administration including the date, time, and dose of IMP will be recorded on the eCRF. The Investigator will make sure that the information entered into the eCRF regarding IMP administration is accurate for each subject. Any reason for noncompliance should be documented.

Noncompliance is defined as a subject missing > 1 administration of trial treatment for nonmedical reasons. If 1 treatment administration was missed and the interval between the subsequent treatment and the last administered treatment is longer than 4 weeks for nonmedical reasons, the criteria of insufficient compliance are met as well. Continuation of treatment should be discussed with the Medical Monitor.

6.10 Blinding

Not applicable.

6.11 Emergency Unblinding

Not applicable.

6.12 Treatment of Overdose

An overdose is defined as any dose 5% greater than the highest dose included in the clinical trial protocol. Any overdose must be recorded in the trial medication section of the eCRF.

For monitoring purposes, any case of overdose, whether or not associated with an AE (serious or nonserious), must be reported to the Sponsor's Global Drug Safety department in an expedited manner using the Serious Adverse Event Paper Report Form following the same timelines as SAE reporting in addition to entering the Overdose in the AE section of the eCRF (see Section 7.4.1.4).

There are no known symptoms of MSB0011359C overdose to date. The Investigator should monitor closely for AEs should an overdose occur and use his or her clinical judgment in providing symptomatic / supportive care as medically indicated. There is no known antidote for MSB0011359C.

